# 8.4.1.14.2 Scales for Outcome in Parkinson's Disease Sleep (SCOPA-Sleep)

The Scales for Outcome in Parkinson's Disease (SCOPA-Sleep) is one of the secondary efficacy endpoints and will be assessed at baseline (day -1), visit 2 (day 14), and visit 3 (day 42) or early termination.

The SCOPA-Sleep is a specific PD rating scale for assessing night-time sleep (NS) and daytime sleepiness (DS) in the past month (37). The NS subscale addresses NS problems in the past month and includes 5 items with 4 response options. Subjects have to indicate how much they were bothered by particular sleep problems, ranging from 0 (not at all) to 3 (a lot). The 5 items address sleep initiation, sleep fragmentation, sleep efficiency, sleep duration, and early wakening. The maximum score of this scale is 15, with higher scores reflecting more severe sleep problems. One additional question evaluates overall sleep quality on a 7-point scale (ranging from slept very well to slept very badly). The score on this item is not included in the score of the NS scale but is used separately as a global measure of sleep quality. The DS subscale evaluates DS in the past month and includes 6 items with 4 response options, ranging from 0 (never) to 3 (often). Subjects indicate how often they fell asleep unexpectedly, fell asleep in particular situations (while sitting peacefully, while watching TV or reading, or while talking to someone), how often they had difficulty staying awake, and whether falling asleep in the daytime was considered a problem. The maximum score is 18, with higher scores reflecting more severe sleepiness. A SCOPA-Sleep sample questionnaire has been included in Appendix 18.7.

Amendment 04, Final Version 1.0 07/Nov/2018 Page 53 / 142

# 8.4.1.14.3 Parkinson's Disease Sleep Scale (PDSS-2)

The Parkinson's Disease Sleep Scale revised version 2 (PDSS-2) is one of the secondary efficacy endpoints and will be assessed at baseline (day -1), visit 2 (day 14), and visit 3 (day 42) or early termination.

The Parkinson's Disease Sleep Scale (PDSS) is a scale for the assessment of sleep disorders in PD in the past week. The scale has 15 items and subjects mark their response to each item on a 10-cm visual analogue scale (VAS). All PDSS items are focussed on nocturnal sleep, except item 15 which addresses DS. The total score is the sum of the item scores and the maximum is 150.

The Revised Version PDSS-2 was developed in order to extend the spectrum of PDSS regarding nocturnal disabilities and for an easier use for subjects as the answers are rated in 5 categories (from 0 [never] to 4 [very frequent]). PDSS-2 total score ranges from 0 (no disturbance) to 60 (maximum nocturnal disturbance). The scale was originally validated in both English and German, and further language validations were performed by Mapi Research Trust (https://eprovide.mapi-trust.org/instruments/parkinson-s-disease-sleep-scale-2#languages). A PDSS-2 sample questionnaire has been included in Appendix 18.5.

## 8.4.1.14.4 Fatigue Severity Scale (FSS)

The Fatigue Severity Scale (FSS) is used as one of the exclusion criteria, and will be assessed at screening and visit 3 (day 42) or early termination.

The FSS is a self-administered questionnaire with 9 items investigating the severity of fatigue in different situations during the past week. It was developed in 1989 and it is the most commonly used fatigue specific questionnaire with its 9 items ranging from 1 to 7, where 1 indicates strong disagreement and 7 strong agreement, and the final score represents the mean value of the 9 items. A FSS sample questionnaire has been included in Appendix 18.12.

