#### **Main Criteria for Exclusion:**

- (1) Subjects with excessive daytime sleepiness due to conditions other than Parkinson's disease (including narcolepsy)
- (2) Subjects with significant eye disease which may substantially impact the subject's mobility and ability to have eye examination conducted as per investigator's judgement.
- (3) Subjects with a recent history of suicide attempt (defined as an active, interrupted or aborted attempt within the past 1 year), or reports suicidal ideation in the past 3 months as indicated by a positive response on the C-SSRS at screening visit (an answer of 'yes' to any of the 6 questions)
- (4) Subjects with clinical evidence of depression with significant psychiatric comorbidities (Hamilton Rating Scale for Depression HAM-D score ≥ 17; with or without treatment)
- (5) Subjects with evidence of significant Cognitive Impairment (Montreal Cognitive Assessment MoCA score ≤ 22 at screening)
- (6) Subjects with evidence of significant fatigue (Fatigue Severity Scale FSS  $\geq$  36)
- (7) Subjects with high risk of sleep apnoea (Berlin questionnaire with  $\geq 2$  categories where the score is positive)
- (8) Subjects taking any of the following prohibited medications at screening:
  - Alerting agents, including r-modafinil, modafinil or methylphenidate
  - Benzodiazepines
  - Histamine active agents
  - Hypnotics
  - Cholinergics
  - Skeletal muscle relaxants
  - Clozapine
  - Atomoxetine
  - Amitriptyline
  - Any other daytime medications which affect sleep
- (9) Subjects with chronic oral and / or ophthalmic steroidal use
- (10) Subjects with either renal or hepatic impairment defined by laboratory parameters >1.5x age-adjusted limits of normal range
  - Hepatic damage: Alanine aminotransferase [ALT], aspartate aminotransferase [AST], alkaline phosphatase, or total bilirubin
  - Renal damage: Blood creatinine, blood urea nitrogen [BUN], or estimated glomerular filtration rate [eGFR] < 60 mL/min/1.73m^2

Amendment 04, Final Version 1.0
Protocol No.: BB-2001-201b
EudraCT No.: 2017-000877-35
Amendment 04, Final Version 1.0
07/Nov/2018
Page 23 / 142

- (11) Subjects with abnormal ECG time intervals at baseline including QTc (> 450 for males and > 470 for females)
- (12) Subjects with known history of lung malignancy.
- (13) Subjects with known history of abuse of alcohol or other addictive substances in the 6 months prior to inclusion.

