(EDS) (Epworth Sleepiness Score [ESS] > 12 at screening). Stable medication for at least 4 weeks before screening is mandatory regarding medication which may affect sleep (for example, dopaminergics, L-dopa, monoamine oxidase inhibitors, antipsychotics, or hypnotics). The exclusion criteria will exclude subjects with EDS due to conditions other than Parkinson's disease (including narcolepsy and sleep apnoea), any significant eye disease which may have an impact on a subject's mobility (which could hamper the study assessments), clinical evidence of depression (HAM-D score ≥ 17, as a certain degree of depression is shown by most of the PD subjects), positive response on the C-SSRS (an answer of 'yes' to any of the 6 questions), clinical evidence of cognitive impairment (MoCA score  $\leq 22$ , as it could interfere with the study assessments), clinical evidence of fatigue (FSS  $\geq$  36, for similar reasons), any alerting medication (including r-modafinil, modafinil or methylphenidate), benzodiazepines, histamine active agents, clozapine, atomoxetine, skeletal muscle relaxants, or any other daytime medications which affect sleep (in order to avoid any selection bias). Subjects with hepatic, renal, cardiac (ECG, including QTc), or ophthalmological impairment will not be entered into the study. The suicide risk will be assessed (C-SSRS) before and after treatment administration at all study visits including followup following the the FDA Guidance for Industry on Suicidal Ideation and Behavior. BPRS+ (Brief Psychiatric Rating Scale) positive subscale to monitor psychotic symptoms and HAM-D to monitor depression will be assessed at all study visits (including follow-up). These assessments are included because patients with Parkinson's disease are known to be at higher risk of psychosis and depression than the general population. Follow-up procedures for a positive finding on the C-SSRS, or an elevated HAM-D or psychosis scale score will be managed as per the standard of care at the site, including an assessment by the investigator of the need for further mental health evaluation. Vital signs (including blood pressure and heart rate) will be assessed at all study visits (including follow-up) as patients with Parkinson's disease are known to commonly exhibit orthostatis and other cardiovascular changes.

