### 8.2. Exclusion Criteria

A subject will not be eligible for inclusion in this study if any of the following criteria are met:

- (1) Subjects with excessive daytime sleepiness due to conditions other than Parkinson's disease (including narcolepsy)
- (2) Subjects with significant eye disease which may substantially impact the subject's mobility and ability to have eye examination conducted as per investigator's judgement.
- (3) Subjects with a recent history of suicide attempt (defined as an active, interrupted or aborted attempt within the past 1 year), or reports suicidal ideation in the past 3 months as indicated by a positive response on the C-SSRS at screening visit (an answer of 'yes' to any of the 6 questions)
- (4) Subjects with clinical evidence of depression with significant psychiatric comorbidities (Hamilton Rating Scale for Depression − HAM-D score ≥ 17; with or without treatment)
- (5) Subjects with evidence of significant Cognitive Impairment (Montreal Cognitive Assessment MoCA score ≤ 22 at screening)
- (6) Subjects with evidence of significant fatigue (Fatigue Severity Scale  $FSS \ge 36$ )
- (7) Subjects with high risk of sleep apnoea (Berlin questionnaire with  $\geq 2$  categories where the score is positive)
- (8) Subjects taking any of the following prohibited medications at screening:
  - Alerting agents, including r-modafinil, modafinil or methylphenidate
  - Benzodiazepines
  - Histamine active agents
  - Hypnotics
  - Cholinergics
  - Skeletal muscle relaxants
  - Clozapine
  - Atomoxetine
  - Amitriptyline
  - Any other daytime medications which affect sleep
- (9) Subjects with chronic oral and / or ophthalmic steroidal use
- (10) Subjects with either renal or hepatic impairment defined by laboratory parameters >1.5x age-adjusted limits of normal range

Protocol No.: BB-2001-201b EudraCT No.: 2017-000877-35 Amendment 04, Final Version 1.0 07/Nov/2018 Page 45 / 142

- Hepatic damage: Alanine aminotransferase [ALT], aspartate aminotransferase [AST], alkaline phosphatase, or total bilirubin
- Renal damage: Blood creatinine, blood urea nitrogen [BUN], or estimated glomerular filtration rate [eGFR] < 60 mL/min/1.73m2
- (11) Subjects with abnormal ECG time intervals at baseline including QTc (> 450 for males and > 470 for females)
- (12) Subjects with known history of lung malignancy.
- (13) Subjects with known history of abuse of alcohol or other addictive substances in the 6 months prior to inclusion.

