18.13. Fatigue Severity Scale (FSS)

#### Fatigue Severity Scale (FSS) of Sleep Disorders

The Fatigue Severity Scale (FSS) is a method of evaluating the impact of fatigue on you. The FSS is a short questionnaire that requires you to rate your level of fatigue.

The FSS questionnaire contains nine statements that rate the severity of your fatigue symptoms. Read each statement and circle a number from 1 to 7, based on how accurately it reflects your condition during the past week and the extent to which you agree or disagree that the statement applies to you.

- A low value (e.g., 1) indicates strong disagreement with the statement, whereas a high value (e.g., 7) indicates strong agreement.
- It is important that you circle a number (1 to 7) for every question.

FSS Questionnaire								
During the past week, I have found that:	Disagree <> Agree							
My motivation is lower when I am fatigued.	1	2	3	4	5	6	7	
Exercise brings on my fatigue.	1	2	3	4	5	6	7	
I am easily fatigued.	1	2	3	4	5	6	7	
Fatigue interferes with my physical functioning.	1	2	3	4	5	6	7	
Fatigue causes frequent problems for me.	1	2	3	4	5	6	7	
My fatigue prevents sustained physical functioning.	1	2	3	4	5	6	7	
Fatigue interferes with carrying out certain duties and responsibilities.	1	2	3	4	5	6	7	
Fatigue is among my three most disabling symptoms.	1	2	3	4	5	6	7	
Fatigue interferes with my work, family, or social life.	1	2	3	4	5	6	7	
			Tot	al Sc	ore:			

Copyright Lauren B. Krupps. Reproduced with permission of the author.

Amendment 04, Final Version 1.0
Protocol No.: BB-2001-201b 07/Nov/2018
EudraCT No.: 2017-000877-35 Page 141 / 142

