9.2.9 Fatigue Severity Scale (FSS)

Mean absolute change in the Fatigue Severity Scale, as defined below.

The FSS is a self-administered questionnaire with 9 items investigating the severity of fatigue in different situations during the past week. There are 9 items ranging from 1 to 7, where 1 indicates strong disagreement and 7 strong agreement, and the final score is calculated as the mean value of the 9 items. If more than 75% of the items are missing then the FSS total score will not be calculated as will be considered as not evaluable. This threshold could be re-evaluated in advance to the data base lock according to the missingness rate in the data

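### The FSS exclusion cut-off of 36 or more cannot be reached on the FSS score as the protocol and SAP define it (an item mean, range 1 to 7); it works only on the item sum, and neither document says which score applies

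*Protocol*

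**What the plan says.** The exclusion is stated three times with the same number. Section 8.2 criterion 6 covers "Subjects with evidence of significant fatigue (Fatigue Severity Scale" score of 36 or more, and the synopsis has the same criterion. Section 7.2 gives the rationale as "clinical evidence of fatigue (FSS $\geq$ 36, for similar reasons", meaning that fatigue, like cognitive impairment, could interfere with the study assessments.

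The score is defined twice, also consistently. Protocol 8.4.1.14.4, which introduces the FSS as an exclusion tool, describes "9 items ranging from 1 to 7, where 1 indicates strong disagreement and 7 strong agreement" and then states that "the final score represents the mean value of the 9 items". SAP 9.2.9 says that "the final score is calculated as the mean value of the 9 items". Its missing-item sentence nevertheless calls the same quantity a total score, and treats it as not evaluable only when more than 75% of items are missing.

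The form in Appendix 18.13 tells the subject "Read each statement and circle a number from 1 to 7", asks for an answer to every question, and ends with a Total Score field. It does not mention averaging. Section 8.4.1.14.4 points to Appendix 18.12 for this form, but that appendix holds the C-SSRS; the FSS form is in 18.13.

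**The concern.** The threshold and the score are on different scales. A rule that compares the defined score with 36 can never be met, and neither document says that eligibility uses the sum while the endpoint uses the mean. The mean cannot be read as applying to the endpoint alone, because the protocol section that defines it presents the FSS as an exclusion instrument.

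Three things depend on the answer:

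- **Eligibility.** Section 8.0 requires the criteria to be assessed at screening, reconfirmed during the baseline period and recorded in the eCRF. A check written from the defined score would pass everyone.
- **Per-protocol set.** Protocol 10.1 makes violation of an entry criterion a major deviation, and SAP section 6 lists inclusion and exclusion criteria among the evaluability aspects. A check on the mean would never flag an FSS violation.
- **Secondary endpoint.** The 6-week FSS change is analysed by ANCOVA (SAP 10.2). The units of the reported effect depend on which score is used.

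**Working it through.** The documents give no derivation of 36, so there is no figure to reproduce. The check is whether 36 lies within the range of each candidate score.

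**Inputs**
- Cut-off: 36 or more (protocol synopsis, 7.2, 8.2).
- Items: nine, each 1 to 7 (protocol 8.4.1.14.4, Appendix 18.13, SAP 9.2.9).
- Score: item mean (protocol 8.4.1.14.4, SAP 9.2.9).
- Missing items: no score if more than 75% are missing (SAP 9.2.9).

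**Step 1. Score as defined (mean).** Minimum = (9 × 1)/9 = 1. Maximum = (9 × 7)/9 = 7. A mean of 36 would need an item sum of 36 × 9 = 324, against a maximum sum of 9 × 7 = 63. Of all 7^9 = 40,353,607 possible response patterns, none reaches 36. Averaging only the answered items does not help, because that mean is also at most 7.

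**Step 2. Alternative score (sum).** Minimum = 9 × 1 = 9. Maximum = 9 × 7 = 63. The cut-off of 36 lies inside this range and corresponds to a mean of 36/9 = 4.0.

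**Step 3. Endpoint with complete items.** Sum = 9 × mean, so change in sum = 9 × change in mean. Multiplying both the outcome and the baseline covariate by 9 multiplies the LS means and confidence limits by 9. The test statistics and p-values stay the same.

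**Step 4. Missing items.** Six of nine missing is 66.7%, so the SAP allows a score. Seven of nine is 77.8%, so it does not. A score can therefore rest on as few as three answers. If the answered items are simply added, the largest possible sum is 7 × (number answered):

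| Items answered | Largest unprorated sum | Can reach 36? |
|---|---|---|
| 3 | 21 | no |
| 4 | 28 | no |
| 5 | 35 | no |
| 6 | 42 | yes |
| 9 | 63 | yes |

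A subject who answers five items, all with 7, has an unprorated sum of 35 and is below the cut-off. The mean of the answered items is 7, which is above the equivalent value of 4.0. With missing items, sum and mean can therefore lead to opposite eligibility decisions.

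**The case against.** The strongest reply is that the intended scale can be inferred. The form has a Total Score field, and a site told to apply a cut-off of 36 to that form would most naturally compare the total. A threshold about five times the maximum mean (36/7 = 5.1) is also more likely to be noticed than to fail silently, and the blinded evaluability meeting in SAP section 6 is a further chance to catch it. On this view the plan has a loose scoring description, and the exclusion itself works.

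Most of this stands, and it limits the consequence. A reader might infer that fatigued subjects will be enrolled. The documents do not support that: they contain no eCRF derivation or edit check based on the mean, and the form points to the sum. A reader might also infer that the cut-off and the reported endpoint cannot be compared. That is wrong when all items are answered, because the conversion is exactly a factor of nine.

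The conflict itself remains. Two sections define the score as a mean, three places give a threshold that this score cannot reach, and the form suggests a different score without saying that eligibility uses it. An inference from a field label does not replace a stated rule for an exclusion criterion, and it does not settle missing items.

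**Conclusion.** The point holds as an internal inconsistency in a decision rule. The cut-off of 36 or more is unattainable on the defined FSS score (maximum 7) and attainable on the item sum (9 to 63), where it equals a mean of 4.0. Read literally, the stated scoring would exclude 0% of subjects. If sites compare the form total, the criterion operates. The documents do not show which happens, so the 0% is the consequence of a literal reading and not a forecast.

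The effect is limited to eligibility screening, per-protocol membership and the scale of one secondary endpoint. The primary ESS analysis is in the ITT set (SAP 9.4), and neither document uses the FSS to define that set. With complete items, the choice of scale leaves the p-values for FSS change unchanged. With missing items, it can change both the score and the eligibility decision.

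The conclusion rests on the item range and count, which the protocol, SAP and form all give alike, and on no statement elsewhere in the documents separating an eligibility score from an endpoint score. It makes no judgement on the clinically right cut-off.

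**What to change.** Reconcile the protocol synopsis (exclusion 6), 7.2, 8.2, 8.4.1.14.4 and Appendix 18.13 with SAP 9.2.9:

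- State whether the eligibility check and the per-protocol check use the item sum or the item mean, and express the cut-off on that scale in every place that gives it.
- State which of the two the 6-week change endpoint uses. If it differs from the eligibility score, say so and give the conversion (sum = 9 × mean with complete items).
- In SAP 9.2.9, use one name for the score in place of both mean and total score. State how it is formed when items are missing, including whether a sum is prorated, and whether the 75% rule also applies to the screening score used for eligibility.
- Label the Total Score field on the form to match.
- Correct the appendix reference in 8.4.1.14.4 from 18.12 to 18.13.

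The cost is about one sentence in each document plus the matching labels. It needs no new data and no change to the sample size or the primary analysis.

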# 8.4.1.14.5 Berlin Questionnaire (BQ)

The Berlin Questionnaire (BQ) is used as one of the exclusion criteria, and will be assessed at screening only.

The BQ is a self-administered and validated questionnaire to be used as a screening tool to identify persons in the community who are at high risk for sleep apnoea. The questionnaire consists of 3 categories (questions 2 to 6 about snoring [category 1], questions 7 to 9 about daytime somnolence [category 2], and question 10 about hypertension and BMI [category 3]) and the risk is based on the responses to individual items and overall scores in the symptom categories (high risk is assessed with 2 or more categories where the score is positive). A BQ sample questionnaire has been included in Appendix 18.14.

# **8.4.1.15** Clinician-Reported Outcome Instruments

The following assessments will be performed by qualified personnel (rater) as indicated in the schedule of procedures. Rater qualification, certification and training required for any rater and/or investigator who will be administering outcomes in this study will be provided

Protocol No.: BB-2001-201b EudraCT No.: 2017-000877-35 Amendment 04, Final Version 1.0 07/Nov/2018 Page 54 / 142

Qualified personnel (rater) will complete the Unified Parkinson's Disease Rating Scale (UPDRS Part III), Cognitive Impairment (Montreal Cognitive Assessment – MoCA), Columbia-Suicide Severity Rating Scale (C-SSRS), Brief Psychiatric Rating Scale Positive Subscale (BPRS+), and the Hamilton Rating Scale for Depression (HAM-D) at the time points specified in the schedule of events (see Appendix 18.15).

# 8.4.1.15.1 Unified Parkinson's Disease Rating Scale (UPDRS Part III)

The Unified Parkinson's Disease Rating Scale Part III (UPDRS Part III) is one of the secondary efficacy endpoints and will be assessed at baseline (day -1), visit 2 (day 14), and visit 3 (day 42) or early termination. Patients will be instructed to have already taken their normally scheduled dose of anti-parkinsonian medication and their IMP prior to arriving at the study site in order to have their UPDRS Part III evaluated in ON (within approximately 1 to 3 hours after taking their levodopa dose). UPDRS in OFF will not be evaluated.

The UPDRS is the most widely used clinical rating scale for PD. The UPDRS was originally developed in 1987, and a new version was sponsored in 2001 by the Movement Disorder Society in order to retain the strengths of the original scale, but resolving identified problems and especially incorporating a number of clinically pertinent PD-related problems poorly captured in the original version. The original four component (Parts I-IV) design was retained, but the focus of each part was changed. Part I concerns "non-motor experiences of daily living", Part II concerns "motor experiences of daily living", Part III is retained as the "motor examination", and Part IV concerns "motor complications". Rater involvement time for administering the UPDRS is estimated to require less than 15 minutes for Part III. Each question is anchored with five responses that are linked to commonly accepted clinical terms of 0 (normal), 1 (slight), 2 (mild), 3 (moderate), and 4 (severe). Part III contains 33 scores based on 18 items, several with right, left or other body distribution scores. An UPDRS Part III sample questionnaire has been included in Appendix 18.8.

